8 ASSESSMENT OF SAFETY

For the timing of safety assessments in this study, refer to the schedule of events in [Table 1](#) and [Table 2](#).

The principal Investigator is responsible for the safety of subjects included in the study. The safety of this study will be overseen by an overarching and independent Data Safety Monitoring Committee Board.

8.1 Safety Endpoints

The safety and tolerability of OTL-101 will be assessed throughout the study by evaluating AEs, clinical laboratory test results, vital signs measurements, ECG, physical examination results, and concomitant medication usage. This will include the occurrence of events related to safety:

- Grade 3/4 procedure-related AEs, including GvHD.
- Episodes of severe and opportunistic infections.
- Clinical laboratory toxicities, including myelosuppression, abnormal blood cell counts and/or biochemistry parameters, according to AE grading scale described in [Section 8.2.1.4](#).
- Toxicity related to the use of LV, specifically the emergence of replication competent lentivirus or monoclonal expansion or leukemia, due to vector insertion.

The safety assessments are described in [Section 8.2](#).

8.2 Safety Assessments

8.2.1 Adverse Events

Adverse events will be monitored and recorded from the time that the subject's parents/legal guardians provide informed consent and then throughout the study (see [Section 3.5](#) for definition of the study duration) and will be elicited by direct, non-leading questioning or if spontaneously reported by the subject/parent/legal guardian. Further details on AE reporting can be found in [Section 8.2.2](#).

An AE is the development of an undesirable medical condition or the deterioration of a pre-existing medical condition following or during exposure to a pharmaceutical product, whether or not it is considered to be causally related to the product. An undesirable medical condition can be symptoms (e.g. nausea, chest pain), signs (e.g. tachycardia, enlarged liver) or the abnormal results of an investigation (e.g. laboratory findings, ECG). In clinical studies an AE can include an undesirable medical condition occurring at any time, including run in or washout periods, even if no OTL-101 has been administered.

Death due to disease progression will be recorded as part of the efficacy evaluation (due to failure of the OTL-101 product) and will be regarded as an SAE unrelated to OTL-101.

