1.4.2.3 Potential Risks Related to Concomitant Therapy

Busulfan

Busulfan is used for conditioning prior to the re-infusion of the HSCs. The Busulfan dose to be used in this clinical study will target a specific area under the curve (AUC), which will ensure more precise dosing and may reduce the risks of toxicity. The risks attached to Busulfan are minimal, although there is a very small possibility of Busulfan-related cancer.

More common risks associated with Busulfan at higher doses include nausea, vomiting, diarrhoea, constipation, loss of appetite, mouth sores, stomach/abdominal pain, dizziness, swelling ankles/feet/hand, flushing, headache, trouble sleeping and a period of neutropaenia. However, the above systemic side-effects have not been seen at the proposed Busulfan dose for this study.

In the Sponsor's experience to date, there have been no Busulfan-related serious adverse events (SAEs).

Pegylated-ADA

The withdrawal of PEG-ADA, which is required 1 month after OTL-101 administration, can have adverse effects on immunity, as well as on other organ systems. It is possible that a very severe infection may develop during this time, which could be fatal if the subject does not respond to OTL-101 infusion.

In the Sponsor's experience to date, there have been no severe infections nor causalities, related to stopping PEG-ADA ERT, 1 month after OTL-101 infusion as per protocol.

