3.6 Stopping Rules and Discontinuation Criteria

3.6.1 Subject Stopping Rules and Criteria for Discontinuation

If any one of the following instances occur, all new enrollments to the protocol or the treatment of subjects will be halted, pending investigation of the cause and discussion with the DSMB for final recommendation/decision:

1. If there is one death or two Grade 4 treatment-related toxicities (see [Section 8.2.1.1](#) for severity definitions). Please note Grade 4 Busulfan-related hematologic AEs such as transient leukopenia, anemia, thrombocytopenia that are anticipated, and have resolved within 42 days of transplant will not be considered a stopping rule.
2. If two subjects experience prolonged unresponsive pancytopenia, defined as an initial failure of hematologic reconstitution which does not improve following the administration of the subject's autologous back-up cells. A failure of hematologic reconstitution is defined as persistent ANC < 200/ μ l or platelets < 20,000/ μ l on three

independent and consecutive determinations over at least ten days after day 42 from the day of OTL-101 infusion.

If, at Day 90 following the initial infusion of OTL-101, the failure of hematologic reconstitution persists after the subject's autologous back-up cells have been infused, the subject can be said to be experiencing prolonged unresponsive pancytopenia. The subject should then receive standard care for pancytopenia.

3. If RCL is detected, and confirmed in one subject.
4. If a subject in the study develops hematological proliferative, monoclonal expansion or malignant disease (excluding dermatofibrosarcoma protuberans (DFSP)). A thorough investigation of the cause of the proliferation, expansion or malignancy, including proviral integration analysis, will be carried out.
5. If there are three non-responders, as defined in the primary endpoint criteria ([Section 3.2.1](#)), who will be designated an OTL-101 treatment failure and will be withdrawn from the study to permit further treatment with PEG-ADA ERT, or HSCT if available.

Any such finding will be discussed with the Sponsor and DSMB, and an agreement should be made and documented to detail the conditions under which the study can be resumed before enrolling the next subject. Evaluations of the study endpoints of subjects already enrolled and who have received OTL-101, will continue.

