8.2.1.2 Causality Classification

The relationship between an AE and study product administration will be classified according to the following:

Related: reports that contain good reasons and sufficient information (e.g. plausible time sequence, dose response relationship, pharmacology, positive de-challenge and/or re-challenge) to assume a causal relationship with OTL-101 administration in the sense that it is plausible, conceivable or likely.

Not related: reports that contain good reasons and sufficient information (e.g. implausible time sequence and/or attributable to concurrent disease or other drugs) to rule out a causal relationship with OTL-101 administration.

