8.2.2 Recording and Follow up of Adverse Events

At each study visit, the subject (or parent/legal guardian) should be asked a non-leading question such as: "How have you felt since transplantation (or last visit)?" All observed or voluntarily reported AEs, regardless of their potential causal relationship with OTL-101, will be recorded on the AE page(s) of the eCRF. Events involving drug reactions, accidents,

illnesses with onset during the study, or exacerbations of pre-existing illnesses should be recorded. Any AEs already recorded and designated as 'continuing' should be reviewed at each subsequent assessment.

Any AEs reported at visits to the subject's general practitioner must be transmitted by the healthcare professional to the responsible investigational site staff, if possible on the same day, so that they can be recorded in the eCRF, notified to the Sponsor (if an SAE), and followed up appropriately by the responsible investigational site staff.

For all AEs, the Investigator must pursue and obtain information that is adequate both to determine the outcome of the AE and to assess whether it meets the criteria for classification as an SAE requiring immediate notification to the Sponsor or its designated representative. For all AEs, sufficient information should be obtained by the Investigator to make an assessment of the causality of the AE (i.e. protocol treatment or other illness). The Investigator is required to assess causality and record that assessment on the eCRF. Follow up of the AE, after the date of OTL-101 infusion, is required if the AE or its sequelae persist. Follow up is required until the event or its sequelae resolve or stabilize at a value acceptable to the Investigator and the Sponsor's clinical monitor or his/her designated representative.

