- Hospitalization is defined as any in-patient admission (even if less than 24 hours). For chronic or long term in-patients, in-patient admission also includes transfer within the hospital to an acute/intensive care in-patient unit.
- Prolongation of hospitalization is defined as any extension of an in-patient hospitalization beyond the stay anticipated/required in relation to the original reason for the initial admission, as determined by the Investigator or treating physician. For protocol specified hospitalization in clinical studies, prolongation is defined as any extension beyond the length of stay described in the protocol. Prolongation in the absence of a precipitating, treatment emergent, clinical AE (i.e. not associated with the development of a new AE or worsening of a pre-existing condition) may meet criteria for "seriousness" but is not an adverse experience and thus is not subject to immediate reporting to the Sponsor.
- Preplanned or elective treatments/surgical procedures should be noted in the subject's screening documentation. Hospitalization for a preplanned or elective treatment/surgical procedure should not be reported as an SAE unless there are complications or sequelae which meet the criteria for seriousness as described above.

Any SAE must be reported immediately (within 24 hours), independent of the circumstances or suspected cause, if it occurs or comes to the attention of the Investigator at any time during the study period.

Any AE/SAE with a suspected causal relationship to OTL-101 administration occurring at any other time after completion of the study must be promptly reported. The following information is the minimum that must be provided to Sponsor's pharmacovigilance contact within 24 hours for each SAE:

- Study number
- Center number
- Subject number
- AE
- Investigator's name and contact details

The additional information included in the SAE form must be provided to the Sponsor or nominated representative as soon as it is available. The Investigator should always provide an assessment of causality for each event reported to the Sponsor. Upon receipt of the initial report, the Sponsor will ask for the Investigator's causality assessment if it was not provided with the initial report.

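### Protocol 8.2.1 labels deaths from disease progression as unrelated to OTL-101 in advance, against the protocol's own case-by-case causality rules

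*Protocol*

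**What the plan says.** Protocol 8.2.1 contains one sentence on this kind of death. It places a death from disease progression under the efficacy evaluation, "due to failure of the OTL-101 product) and will be regarded as an SAE unrelated to OTL-101". Disease progression is not defined there or elsewhere in the protocol.

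Three other sections govern causality, and none makes an exception for these deaths:

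- Protocol 8.2.1.2 has two categories. An event is related if a causal link is at least conceivable. It is not related only if the report holds good reasons and enough information "to rule out a causal relationship with OTL-101 administration".
- Protocol 8.2.2, speaking of all AEs: "The Investigator is required to assess causality and record that assessment on the eCRF".
- Protocol 8.2.3, on SAEs: "The Investigator should always provide an assessment of causality for each event reported to the Sponsor".

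Two risk statements bear on the matter. Protocol 1.4.2.1 lists failure of the treatment among the major risks of OTL-101. Protocol 1.4.2.3 warns of a severe infection after PEG-ADA is withdrawn, "which could be fatal if the subject does not respond to OTL-101 infusion".

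The first halting criterion in Protocol 3.6.1 reads "If there is one death or two Grade 4 treatment-related toxicities".

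**The concern.** The sentence in 8.2.1 blames the product for the death and then declares the death unrelated to the product. Whether a given death is related is a judgement on the facts of that case, and the rest of the protocol treats it so. A fixed label replaces that judgement for a class of deaths whose limits are not stated.

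The label has consequences because two outputs depend on relatedness: the treatment-related summaries planned in SAP 8.4.1.2 (and the tables by relationship in Protocol 9.6.5), and the SUSAR route in Protocol 8.2.7, which starts from a suspected reaction. With ten subjects and few events, the classification of one death is visible in the safety results.

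The undefined term adds to the difficulty. Protocol 7.2 describes infections as a feature of ADA-SCID as well as a safety matter, and Protocol 8.1 makes severe and opportunistic infections a safety endpoint. Protocol 8.2.5 asks for the leading cause of death as the AE term and gives pneumonia as an example. A fatal infection in a subject whose immune system has not recovered could be filed as disease progression, and so be unrelated by rule. It could equally be filed as pneumonia and assessed in the ordinary way.

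**Working it through.** The plan gives no figure on this point, so there is none to reproduce. The check is a comparison of texts, followed by a small illustration of size.

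**1. Process.** Protocol 8.2.1 fixes the result for a class of deaths. Protocol 8.2.2 and 8.2.3 require an individual assessment by the investigator for every event. Both cannot be followed for the same death: either the assessment is made and may differ from the label, or the label makes it empty.

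**2. Standard.** Protocol 8.2.1.2 needs case-level information before a link is excluded. The sentence in 8.2.1 supplies none, and its bracket points to the product as the reason for the death.

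**3. What the label removes.**
- SAP 8.4.1.2, overall summary: the lines for treatment-related AEs and treatment-related SAEs.
- SAP 8.4.1.2, table of treatment-related AEs by system organ class and preferred term.
- Protocol 8.2.7: consideration as a SUSAR, because the event is no longer a suspected reaction.

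**4. What the label leaves in place.**
- Protocol 8.2.3 and 8.2.5: the 24-hour report to the sponsor, which applies to every SAE and every fatal AE whatever the relationship.
- SAP 8.4.1.2: the lines for any SAE and for SAEs leading to death, and the SAE table if there are enough events to produce it.
- SAP 8.3.1.2 and 8.3.1.3: death counts in overall and event-free survival.

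**5. Size.** Input: n = 10 treated subjects (Protocol 9.4). Assumptions: one such death, which the investigator would have judged related, in a subject with no other related SAE.
- Contribution to the treatment-related SAE line under the current text: 0 of 10 = 0%.
- Contribution with an individual assessment: 1 of 10 = 10%.
- Line for SAEs leading to death: 1 of 10 = 10% either way.

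If the subject already has another related SAE, or the investigator judges the death unrelated, the first line does not move. The change is therefore at most 10 percentage points per death.

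For scale only, exact 95% intervals for related fatal SAEs would be:
- 0/10: upper limit 1 − 0.025^(1/10) = 30.8%, so 0 to 30.8%.
- 1/10: lower limit 1 − 0.975^(1/10) = 0.3%; the upper limit solves (1 − p)^10 + 10p(1 − p)^9 = 0.025, giving 44.5%.

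The SAP plans neither a line for related fatal SAEs nor intervals for adverse events, so these intervals describe no planned output.

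**The case against.** The strongest defence is that the classification may be right. Protocol 8.2.1.2 itself gives attribution to a concurrent disease as a ground for calling an event unrelated, and a death from ADA-SCID arguably fits. Protocol 4.4 and 8.2.6 also separate insufficient response from adverse events, and the fatal-infection warning in 1.4.2.3 concerns the withdrawal of PEG-ADA, not the infusion. This stands in part: many such deaths might properly be judged unrelated. But the example in 8.2.1.2 is a kind of evidence to be weighed in a case, and the sentence in 8.2.1 does away with the weighing.

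A reader might infer that these deaths escape expedited reporting or vanish from the safety results. The documents do not support that. The 24-hour report is required regardless of relationship, and the any-SAE and fatal-SAE lines do not depend on it. Only the SUSAR route is closed, and Protocol 8.2.7 also provides for other important safety reports.

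Nor do the documents show that a SUSAR report would actually be lost. A SUSAR must also be unexpected, and Protocol 8.1.2.3's counterpart on expectedness, Protocol 8.2.1.3, judges that against the Investigator's Brochure, which is not available here. Protocol 1.4.2.1 says that the listed risks, including treatment failure, are described in it. What the label removes is the chance to consider the question.

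On 3.6.1, the adjective sits next to the toxicities, so the more natural reading is that it does not limit the death. The wording still permits the other reading.

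**Conclusion.** The point holds as an internal contradiction with limited but real effect. Protocol 8.2.1 sets an outcome that 8.2.1.2, 8.2.2 and 8.2.3 leave to individual assessment, and it does so for an undefined class of deaths. Each such death would be missing from the treatment-related summaries, a change of at most one subject in ten, and could not be considered as a SUSAR. All-cause fatal counts and 24-hour reporting are unaffected.

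This assumes that the sentence is applied literally and that at least one such death occurs. The survival endpoints capture a death during the study. They may miss one after withdrawal, since SAP 8.3.1.2 gives unknown status to a subject withdrawn alive before 12 months.

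A reader might also conclude that the plan hides the gravest fatal risk of the product. The documents name non-response as potentially fatal but do not rank it against other risks, so that conclusion goes too far.

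The 3.6.1 question is separate and secondary. If relatedness did limit the one-death criterion, the label in 8.2.1 could keep such a death from meeting it; if it did not, the label would have no bearing.

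**What to change.** In Protocol 8.2.1, delete the closing clause, which says that the death "will be regarded as an SAE unrelated to OTL-101". State that these deaths receive an individual causality assessment under 8.2.1.2, like any other SAE. They can still be recorded under efficacy. Their status as SAEs does not depend on the deleted clause, because 8.2.3 and 8.2.5 already secure it.

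Separately, the sponsor should reconcile 3.6.1 with 8.2.1 so that it is clear whether the one-death criterion depends on relatedness. Which reading applies is for the sponsor to decide.

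The cost is a change of protocol wording. It needs no new data and no change to the SAP tables. The small downside is that a few more events may be classed as related SAEs or sent as expedited reports.

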8.2.1.1 Severity Classification of Adverse Events

Adverse events will be recorded and graded according to an adapted Pediatric Clinical Toxicity Scale from the National Institute Allergy and Infectious Diseases (NIAID), Autoimmuno-deficiency Syndrome (AIDS) Division (see [Section 17: Appendix 3](#)):

Grade 1 (Mild): Symptoms causing no or minimal interference with usual social & functional activities.

Grade 2 (Moderate): Symptoms causing greater than minimal interference with usual social & functional activities.

Grade 3 (Severe): Symptoms causing an inability to perform usual social & functional activities.

Grade 4 (Life threatening): Symptoms causing an inability to perform basic self-care functions OR medical or operative intervention indicated to prevent permanent impairment, persistent disability, or death.

Grade 5 (Death)

8.2.1.2 Causality Classification

The relationship between an AE and study product administration will be classified according to the following:

Related: reports that contain good reasons and sufficient information (e.g. plausible time sequence, dose response relationship, pharmacology, positive de-challenge and/or re-challenge) to assume a causal relationship with OTL-101 administration in the sense that it is plausible, conceivable or likely.

Not related: reports that contain good reasons and sufficient information (e.g. implausible time sequence and/or attributable to concurrent disease or other drugs) to rule out a causal relationship with OTL-101 administration.

8.2.1.3 Assessment of Expectedness

The reference document used to assess the expectedness of AEs in this study will be the current IB.

8.2.1.4 Laboratory Test Abnormalities

Abnormalities in laboratory test values should only be reported as AEs if any of the following apply:

- They result in a delay of the OTL-101 treatment or other study procedures,
- They require an intervention or diagnostic evaluation to assess the risk to the subject,
- They are considered to be clinically significant by the Investigator.

8.2.1.5 Abnormal Physical Examination Findings

In the judgment of the Investigator, clinically significant changes to the findings of physical examinations (abnormalities) will be recorded as AEs.

8.2.1.6 Other Investigation Abnormal Findings

Abnormal test findings judged by the Investigator to be clinically significant (e.g. ECG, echo changes) and that require an intervention or diagnostic evaluation to assess the risk to the subject, should be recorded as AEs.

8.2.2 Recording and Follow up of Adverse Events

At each study visit, the subject (or parent/legal guardian) should be asked a non-leading question such as: "How have you felt since transplantation (or last visit)?" All observed or voluntarily reported AEs, regardless of their potential causal relationship with OTL-101, will be recorded on the AE page(s) of the eCRF. Events involving drug reactions, accidents,

illnesses with onset during the study, or exacerbations of pre-existing illnesses should be recorded. Any AEs already recorded and designated as 'continuing' should be reviewed at each subsequent assessment.

Any AEs reported at visits to the subject's general practitioner must be transmitted by the healthcare professional to the responsible investigational site staff, if possible on the same day, so that they can be recorded in the eCRF, notified to the Sponsor (if an SAE), and followed up appropriately by the responsible investigational site staff.

For all AEs, the Investigator must pursue and obtain information that is adequate both to determine the outcome of the AE and to assess whether it meets the criteria for classification as an SAE requiring immediate notification to the Sponsor or its designated representative. For all AEs, sufficient information should be obtained by the Investigator to make an assessment of the causality of the AE (i.e. protocol treatment or other illness). The Investigator is required to assess causality and record that assessment on the eCRF. Follow up of the AE, after the date of OTL-101 infusion, is required if the AE or its sequelae persist. Follow up is required until the event or its sequelae resolve or stabilize at a value acceptable to the Investigator and the Sponsor's clinical monitor or his/her designated representative.

